3.6.1 Secondary Statistical Hypotheses

The specified set of secondary effectiveness hypotheses involve the assessment of the following statistical hypotheses:

- 1. VERSE (standardised, daily very early) aphasia therapy will result in greater improvements in communication ability than UC-Plus (non-standardised daily very early), as measured by the WAB-R (AQ),² at 12 weeks post stroke.
- 2. VERSE (standardised, daily very early) aphasia therapy will result in greater improvements in ability than UC-Plus (non-standardised daily very early), as measured by the WAB-R (AQ),² 26 weeks post stroke.
- 3. VERSE (standardised, daily very early) aphasia therapy will result in greater improvements in communication ability than Usual Care alone (UC), as measured by the WAB-R (AQ),² 12 weeks post stroke.
- 4. VERSE (standardised, daily very early) aphasia therapy will result in greater improvements in communication ability than Usual Care alone (UC), as measured by the WAB-R (AQ),² 26 weeks post stroke.
- 5. UC-Plus (non-standardised daily very early) will result in greater improvements in communication ability than Usual Care alone (UC), as measured by the WAB-R (AQ),² 12 weeks post stroke.

- 6. UC-Plus (non-standardised daily very early) will result in greater improvements in communication ability than Usual Care alone (UC), as measured by the WAB-R (AQ),² 26 weeks post stroke.
- 7. VERSE (standardised, daily very early) aphasia therapy will result in greater improvements in connected speech than UC-Plus (non-standardised daily very early), as measured by Discourse Analysis,¹⁰⁻¹⁶ 12 weeks post stroke.
- 8. VERSE (standardised, daily very early) aphasia therapy will result in greater improvements in connected speech than UC-Plus (non-standardised daily very early), as measured by Discourse Analysis,¹⁰⁻¹⁶ 26 weeks post stroke.
- 9. VERSE (standardised, daily very early) aphasia therapy will result in greater improvements in connected speech than Usual Care alone (UC), as measured by Discourse Analysis,¹⁰⁻¹⁶ 12 weeks post stroke.
- 10. VERSE (standardised, daily very early) aphasia therapy will result in greater improvements in connected speech than Usual Care alone (UC), as measured by Discourse Analysis,¹⁰⁻¹⁶ 26 weeks post stroke.
- 11. UC-Plus (non-standardised daily very early), will result in greater improvements in connected speech than Usual Care alone (UC), as measured by Discourse Analysis,¹⁰⁻¹⁶ 12 weeks post stroke.
- 12. UC-Plus (non-standardised daily very early), will result in greater improvements in connected speech than Usual Care alone (UC), as measured by Discourse Analysis,¹⁰⁻¹⁶ 26 weeks post stroke.

3.6.2 Analysis Methods:

The outcome measure for all effectiveness analyses that involve WAB-R $(AQ)^2$ will be %MPR.¹⁶ For outcomes assessed at 12 weeks post stroke, this will be %MPR¹⁶ at 12 weeks post stroke, as defined in section 3.5.1 above. For outcomes assessed at 26 weeks post stroke this will be %MPR¹⁶ at 26 weeks as measured at baseline. That is,

% MPR at 26 weeks =
$$\frac{(AQ \text{ at } 26 \text{ weeks}) - (AQ \text{ at baseline})}{100 - (AQ \text{ at baseline})} X100$$

The outcome measure for all efficacy analyses involving Discourse Analysis^{10,11} will be %CIUs.

3.6.2.1 Comparison between VERSE and UC-Plus groups:

3.6.2.1.1 Communication Outcomes $(WAB-R (AQ)^2)$:

A longitudinal linear mixed model will be used to assess difference between the VERSE and UC-Plus groups on %MPR¹⁶ at 12 weeks and 26 weeks. The main between-group difference at each time point will be assessed through the interaction effect of group and timepoint. The model will adjust for baseline aphasia severity by including the WAB-R (AQ)² score at baseline as a covariate. Baseline stroke severity will be controlled for by including the NIHSS⁴ at baseline as a fixed factor in the model. Recruitment site will be included as a random effect.

3.6.2.1.2 Connected Speech Outcomes (Discourse Analysis):

A similar longitudinal linear mixed model will be used to assess difference between the VERSE and UC-Plus groups on %CIUs¹⁰⁻¹⁶ at 12 weeks and 26 weeks. The main between-group difference at each time point will be assessed through the interaction effect of group and timepoint. The model will adjust for baseline aphasia severity by including the WAB-R (AQ)² score at baseline as a covariate. Baseline stroke severity will be controlled for by including the NIHSS⁴ at baseline as a fixed factor in the model. Recruitment site will be included as a random effect.

3.6.2.2 Comparison with UC group at 12 weeks and 26 weeks:

3.6.2.2.1 Communication Outcomes (WAB-R (AQ^2)):

A longitudinal linear mixed model will be used to compare each of the VERSE and UC-Plus groups to the UC group on %MPR¹⁹ at 12 weeks and 26 weeks. The main between-group difference will be assessed through the interaction effect of group and time point. The model will adjust for baseline aphasia severity by including the WAB-R (AQ)² score at baseline as a covariate. Baseline stroke severity will be controlled for by including the NIHSS⁴ at baseline as a fixed factor in the model. Recruitment site will be included as a random effect.

3.6.2.2.2 Connected Speech Outcomes (Discourse Analysis):

A similar longitudinal linear mixed model will be used to compare each of the VERSE and UC- Plus groups to the UC group on %CIUs¹⁰⁻¹⁶ at 12 weeks and 26 weeks. The main between-group difference at each time point will be assessed through the interaction effect of group and timepoint. The model will adjust for baseline aphasia severity by including the WAB-R (AQ)² score at baseline as a covariate. Baseline stroke severity will be controlled for by including the NIHSS⁴ at baseline as a fixed factor in the model. Recruitment site will be included as a random effect.

3.6.2.3 Handling of Missing Data:

Missing data for secondary analyses will be handled as per section 3.5.3.

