1.6 Baseline and follow-up assessments

All stroke patients with aphasia, who are at least 18 years old, are screened for inclusion in the study. Those screened and deemed ineligible for the study are entered onto a screening log which outlines the reason for non-inclusion. Details of the screening and recruitment procedures, as well as the assessment schedule are included in the main trial protocol.

The assessment timeline is outlined in Figure 1. Baseline assessment occurs no earlier than two days from the onset of stroke and no later than 14 days from the onset of stroke. Participants undergo the (AQ) component of the WAB-R.² Participants are also assessed for their medical and stroke history. Baseline data collection includes the collection and documentation of:

- 1) Demographic details including age, gender, past medical history, languages spoken, education level, handedness, employment, Aboriginal or Torres Strait islander status and living arrangements.
- 2) Stroke type and severity (type, hemisphere, first or recurrent stroke, National Institute of Health Stroke Scale, (NIHSS⁴), modified Rankin Scale (mRS⁵), Oxfordshire Community Stroke Project Classification (OCSP⁶), Royal Brisbane Hospital Outcome Measure for Swallowing (RBHOM⁷) and Australian Therapy outcome measures (AusTOMS⁸).
- 3) Additional baseline assessments including the Boston Naming Test (BNT⁹), the "clock drawing" cognitive sub test, and discourse collection.
- 4) Time of assessment and aphasia therapy commencement.

Therapy commences the day after the baseline assessment, and is completed within a maximum of 25 working days and must be completed by day 50 post stroke.

The participants are followed up at their place of residence or in the hospital clinic by a blinded assessor, 12 weeks and 26 weeks after the date of the stroke. Patient assessments at these follow-up visits include:

- the Aphasia Quotient component of the Western Aphasia Battery-Revised²
- the Boston Naming Test,⁹
- Discourse collection,¹⁰⁻¹⁶
- Stroke and Aphasia Quality of life questionnaire 39 item version¹⁷; and
- The Aphasia Depression Rating Scale.¹⁸

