- National Research Council. 2010. The Prevention and Treatment of Missing Data in Clinical Trials. Washington, DC: The National Academies Press. https://doi.org/10.17226/12955.

Appendix 1

Table 1: Baseline Participant and Stroke Characteristics

	UC	UC+	VERSE	All
	n (%)	n (%)	n (%)	n (%)
Recruitment Region				
Australia				
New Zealand				
Patient Details				
Age Median (IQR)				
<65				
65-80				
>80				
Gender				
Male				
Female				
Pre-morbid History (Living arrangements prior to stroke)				
Home alone				
Home with other				
Supported accommodation				
Unknown				
Stroke Risk Factors				
HTN				
IHD				
AF				
Hypercholesterolaemia				
Diabetes				
Smoking				
Baseline NIHSS, Mean (SD)				
Baseline mRS (binary)				
Low (0-2)				
High (3-6)				
High (3-6) Oxfordshire Stroke Classification				

VERSION 1.1 DATE: 28 March 2018

PACS
POCS
LACS
Haemorrhage
Time to Randomisation (days), Median (IQR)*

*n.b. time calculated from stroke onset to randomisation

Page 22 of 29

	UC	UC+	VERSE	All
	n (%)	n (%)	n (%)	n (%)
Frenchay Aphasia Screening Test Median (IQR)				
Baseline Western Aphasia Battery - Revised AQ Mean (SD)				
Ceiling (93.7 - 100)				
Mild (93.6 - 62.6)				
Moderate (62.5 – 31.3)				
Severe (0 – 31.2)				
Baseline Discourse Measures				
No. of Words, Mean (SD)				
No. CIUs, Mean (SD)				
% CIUs , Mean (SD)				
Boston Naming Test, Mean (SD)				
AuSTOMS				
Dysarthria				
No impairment				
Mild impairment				
Moderate impairment				
Moderate/severe impairment				
Profound impairment				
Apraxia of Speech (AoS)				
No impairment				
Mild impairment				
Moderate impairment				
Moderate/severe impairment				
Profound impairment				
Clock Drawing/Cog Test, Median (IQR) RBHOMS				

Table 2: Baseline communication, swallowing and cognition characteristics

Page 23 of 29

		UC	UC+	VERSE	All
Length of Inpatient Hospital Stay* Median (IQR)					
Time to first therapy,* Median (IQR)					
Received Therapy as Inpatient n (%)					
Met Intervention Compliance n (%)					
Intervention number of Therapy	Usual Ward Care				
Intervention number of Therapy Sessions, Median (IQR)+Usual Ward Care Intense TherapyFrequency: Sessions per week, Median (IQR)Usual Ward Care 	Intense Therapy				
Frequency: Sessions per week,	Usual Ward Care				

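### The connected-speech models leave out baseline %CIUs, which the trial collects, and so give up precision on six secondary hypotheses

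*SAP*

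**What the plan says.** - **Hypotheses.** Statistical hypotheses 7 to 12 in SAP 3.6.1 concern connected speech and are worded as gains. VERSE, for example, "will result in greater improvements in connected speech than UC-Plus"; the others compare VERSE or UC-Plus with usual care, each at 12 and at 26 weeks.
- **Outcome.** SAP 3.6.2 fixes %CIUs as "The outcome measure for all efficacy analyses involving Discourse Analysis". No change score or recovery index is defined for it.
- **Models.** SAP 3.6.2.1.2: "A similar longitudinal linear mixed model will be used to assess difference between the VERSE and UC-Plus groups on" %CIUs at 12 and 26 weeks. SAP 3.6.2.2.2: "A similar longitudinal linear mixed model will be used to compare each of the VERSE and UC- Plus groups to the UC group on" the same outcome and times. In both, "The main between-group difference at each time point will be assessed through the interaction effect of group and timepoint". The other listed terms are baseline WAB-R AQ, baseline NIHSS and a random effect for recruitment site.
- **Baseline data.** SAP 1.6 lists, among the additional baseline assessments, the "cognitive sub test, and discourse collection". Table 2 in Appendix 1 has a block "Baseline Discourse Measures" with rows for number of words, number of CIUs and %CIUs.

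**The concern.** The discourse models are modelled on the WAB-R models, where baseline enters twice: %MPR has baseline AQ in its formula (SAP 3.5.1), and baseline AQ is also a covariate. When the same structure is applied to %CIUs the outcome changes, but its own baseline does not come with it. The follow-up value is analysed with adjustment for a different scale.

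AQ is a broad score covering spoken production and auditory comprehension, so it captures only part of how informative a person's connected speech was at entry. Two things are at stake:

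- Person-to-person variation that baseline %CIUs could explain stays in the residual, which widens the confidence intervals.
- Randomisation is stratified on AQ bands only (SAP 1.4), so a chance difference between arms in baseline discourse beyond AQ is handled neither by the design nor by the model.

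Efficiency matters here because SAP 1.7 supports power for discourse by analogy with pilot effect sizes and gives no calculation.

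**Working it through.** **Is there a figure to reproduce?** Not for discourse. The only sample size in SAP 1.7 is 82 per arm for a 4.4-point difference in %MPR, with 80% power, two-sided 0.05 and 20% loss. No SD or longitudinal correlation is given, so it cannot be reproduced. It can only be solved backwards as a simple two-sample comparison:

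- analysable per arm = 82 × 0.8 = 65.6
- implied SD = 4.4 / [(1.960 + 0.842) × √(2/65.6)] ≈ 9.0 %MPR points

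That figure concerns %MPR and says nothing about the spread of %CIUs.

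**Which terms are in the models?** Setting 3.6.2.1.2 and 3.6.2.2.2 beside 1.6 and Table 2: group, time point and their interaction, AQ, NIHSS and site are in; baseline %CIUs is collected and tabulated, and is in neither model.

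**What would adding it gain?** Let r be the partial correlation of baseline with follow-up %CIUs given the covariates already present. At one follow-up time:

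- residual variance is multiplied by 1 − r²
- the standard error is multiplied by √(1 − r²)
- the equivalent increase in participants is 1/(1 − r²) − 1
- a comparison now at 80% power moves to Φ(2.802/√(1 − r²) − 1.960)

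Every r below is an assumption, and it may differ between 12 and 26 weeks.

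| r | Variance × | SE × | Equivalent extra participants | Power from 80% |
|---|---|---|---|---|
| 0.1 | 0.99 | 0.995 | 1% | 80.4% |
| 0.2 | 0.96 | 0.980 | 4% | 81.6% |
| 0.3 | 0.91 | 0.954 | 10% | 83.6% |
| 0.4 | 0.84 | 0.917 | 19% | 86.4% |
| 0.5 | 0.75 | 0.866 | 33% | 89.9% |
| 0.6 | 0.64 | 0.800 | 56% | 93.8% |

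**How much does AQ already recover?** This can be seen by building r from ordinary correlations, again assumed and with NIHSS left out: baseline with follow-up %CIUs 0.4 to 0.8, AQ with follow-up %CIUs 0.4 to 0.6, AQ with baseline %CIUs 0.5 to 0.7.

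- Least gain (0.4, 0.6, 0.7): r = (0.4 − 0.6 × 0.7)/√(0.64 × 0.51) ≈ −0.035, variance × 0.999. AQ has done all the work.
- Middle case (0.6, 0.5, and 0.5 to 0.7): variance × 0.78 to 0.84, SE 8% to 12% smaller, power from 80% to about 87% to 89%.
- Most gain (0.8, 0.4, 0.7): r = (0.8 − 0.4 × 0.7)/√(0.84 × 0.51) ≈ 0.79, variance × 0.37.

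**Simulation check.** Two arms of 66, no treatment effect, 4,000 runs, correlations given in the same order. Entries are empirical standard errors in SD units.

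| Correlations | AQ only | AQ + baseline %CIUs | Change score, AQ adjusted |
|---|---|---|---|
| 0.5, 0.5, 0.6 | 0.151 | 0.145 | 0.172 |
| 0.6, 0.5, 0.6 | 0.153 | 0.136 | 0.154 |
| 0.7, 0.5, 0.6 | 0.150 | 0.123 | 0.134 |
| 0.8, 0.5, 0.7 | 0.151 | 0.104 | 0.105 |

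The mean estimates from both covariate models lay within 0.005 SD of zero, so neither is biased. The change score is less precise than the current model in the first case and never better than covariate adjustment.

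**The case against.** **The stronger reading.** A reader might infer that, because the hypotheses speak of improvement while the model analyses follow-up %CIUs, the analysis does not measure what it names. The SAP does not support that. Allocation is randomised (1.4), so baseline %CIUs has the same expectation in every arm, and the difference at follow-up estimates the same effect as the difference in change. Covariate adjustment targets that same quantity, so if the present model failed on this ground the remedy would fail too.

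**AQ and NIHSS are a uniform, pre-specified adjustment set.** This is true, and AQ is a partial proxy for connected speech. The outcome is therefore not analysed bare, and any remaining chance imbalance is reflected in the confidence interval. What stands is that the gain may be small; it does not follow that it is nil.

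**Baseline may be meant as a repeated outcome.** SAP 1.7 assumes a longitudinal model with outcomes at three times including baseline, and a group-by-time interaction would then give a difference in change. That sentence is a sample-size assumption. Sections 3.6.2.1.2 and 3.6.2.2.2 name 12 and 26 weeks only, and the WAB-R model they copy could not carry a useful baseline row, since %MPR at baseline is zero by definition.

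**Baseline %CIUs is an awkward covariate.** Assessment falls 2 to 14 days after stroke and the severe stratum reaches AQ 0. Someone who produces no words has an undefined percentage, and someone who produces few has an unstable one. This stands, and means that the remedy needs a stated rule as well as an extra term.

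**Conclusion.** The point holds as a matter of efficiency. The two discourse models are valid and unbiased, but they omit the outcome's own baseline, which is already collected and is given a row in Table 2. They forgo whatever precision it adds beyond AQ and NIHSS, and leave chance imbalance in baseline discourse beyond AQ unadjusted.

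The size cannot be fixed from the SAP. It runs from practically nothing, if baseline %CIUs adds little to AQ and NIHSS, to an SE about 5% smaller at an assumed partial correlation of 0.3, 8% at 0.4 and 20% at 0.6. It would be wrong to state as fact that six hypotheses lose material power. The primary analysis and the %MPR analyses are not affected.

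The case for acting is that the two sides are unequal. If r is small, the cost is one or two degrees of freedom out of roughly 131 analysable participants in a two-arm comparison (2 × 65.6); if r is moderate, the gain is worth having.

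**What to change.** Before unblinding:

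1. In SAP 3.6.2.1.2 and 3.6.2.2.2, add baseline %CIUs as a continuous covariate beside baseline AQ and NIHSS.
2. State how a missing or undefined baseline %CIUs is handled, including the case of no words produced, so that nobody is dropped. In the analysis without imputed outcomes, a fixed fill-in value plus an indicator would do this.
3. Since 3.6.2.3 refers missing data to 3.5.3, include baseline %CIUs in the chained-equations imputation model as well.
4. Do not replace the follow-up outcome with a raw change score, which can be less precise than the current model.

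The cost is a few lines of SAP text and one or two model terms. No new data are needed.

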3.7 Other Secondary Outcomes: Quality of Life

It is hypothesised that:

Very early aphasia therapy (UC-Plus and VERSE) will result in better quality of life at 12 and 26 weeks post stroke than UC control.

3.7.1 Outcome measure for Quality of Life

Quality of life will be assessed using the Stroke and Aphasia Quality of Life Scale (SAQoL).¹⁷

3.7.2 Statistical Hypotheses for Quality of Life

The specified quality of life hypotheses involve the assessment of the following statistical hypotheses:

- 1. Very early daily aphasia therapy (UC-Plus or VERSE) will result in higher quality of life than Usual Care alone at 12 weeks post stroke.
- 2. VERSE aphasia therapy will result in higher quality of life than Usual Care alone at 12 weeks post stroke.
- 3. UC-Plus will result in higher quality of life than Usual Care alone at 12 weeks post stroke.
- 4. VERSE aphasia therapy will result in higher quality of life that UC Plus at 12 weeks post stroke.
- 5. Very early intensive aphasia therapy (UC-Plus or VERSE) will result in greater improvements in communication ability at 26 weeks post stroke.
- 6. VERSE aphasia therapy will result in higher quality of life than Usual Care alone at 26 weeks post stroke.
- 7. UC- Plus will result in higher quality of life than Usual Care alone at 26 weeks post stroke.
- 8. VERSE aphasia therapy will result in higher quality of life that UC Plus at 26 weeks post stroke.

3.7.1 Analysis Method:

Separate linear mixed effects regression model will be used to assess quality of life as measured by the SAQoL¹⁷ at 12 weeks post stroke and at 26 weeks post stroke. Each model will compare the effects of:

- 1. VERSE therapy to usual care alone
- 2. UC- Plus therapy to usual care alone

The model will adjust for baseline aphasia severity by including the WAB-R $(AQ)^2$ score at baseline as a covariate. Baseline stroke severity will be controlled for by including the NIHSS⁴ at baseline as a fixed factor in the model. Recruitment site will be included as a random effect. The treatment effects will be reported as difference in SAQoL¹⁷ (between VERSE and UC and between UC- Plus and UC); the corresponding 95% confidence intervals will be reported.

3.7.1.1 Handling of Missing Data:

Handling of missing data will be similar to the detail in section 3.5.3.

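### The SAQoL models could also adjust for baseline mRS, which is collected but enters no model: an optional and probably small gain in precision

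*SAP*

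**What the plan says.** The Analysis Method for quality of life is the second section numbered 3.7.1, placed after 3.7.2. It plans two models, one for each follow-up time: "Separate linear mixed effects regression model will be used to assess quality of life as measured by the" SAQoL. Each model compares VERSE with UC and UC-Plus with UC.

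Three adjustment terms are given:
- Baseline AQ: "The model will adjust for baseline aphasia severity by including the WAB-R" (AQ).
- Baseline NIHSS, which enters "at baseline as a fixed factor in the model. Recruitment site will be included as a random effect".
- Site, as that same passage says, as a random effect.

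Sections 3.5.4 and 3.6.2 use the same set for %MPR, and 3.6.2 uses it for %CIUs.

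Section 1.6 lists the baseline stroke measures, among them "National Institute of Health Stroke Scale, (NIHSS⁴), modified Rankin Scale (mRS⁵"). SAQoL appears there only among the 12- and 26-week assessments, and Table 2 has no baseline row for it. Section 1.6 also refers the reader to the main protocol for the assessment schedule. In Appendix 1, Table 1, the mRS row is headed "Baseline mRS (binary") and splits the scale into 0-2 and 3-6. No model in the SAP contains mRS.

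**The concern.** For %MPR, baseline AQ is the starting value of the outcome's own scale, so the common covariate set fits that outcome closely. For SAQoL the same set gives language severity and neurological severity. It includes no listed starting value of the outcome and no disability grade. The SAP gives no reason for leaving out mRS, the one such grade it collects.

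Randomisation is stratified by aphasia severity only (1.4), so the design does not force balance on mRS. Covariates that predict the outcome narrow the confidence interval and correct for chance imbalance. In a linear model they do this without changing the mean difference being estimated.

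Precision is also less certain for SAQoL than for the communication outcomes. Section 1.7 says that no quality-of-life pilot data were available and expects sufficient power without an SD, an effect size or a calculation. At stake is the width of the intervals for a secondary outcome, not the validity of the comparison.

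**Working it through.** **Is there a figure in the plan to reproduce?** Not for SAQoL. The 246 participants (82 per arm) in 1.7 are for a 4.4% difference in %MPR. No SD is given for either outcome, and no correlation of mRS with SAQoL.

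**Inputs**
- 82 per arm (1.7), so 164 in a two-arm contrast.
- 13% missing (3.5.3). This is for the primary outcome when the SAP was published, and is used here as a stand-in. 164 × 0.87 = 142.7, about 143.
- 20% planned loss (1.7), as a check. 164 × 0.80 = 131.2.
- Partial R², the share of SAQoL variance left after AQ, NIHSS and site that mRS explains. This is **assumed**: 0-5%, with 10% as an upper case.

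**Formulas**
- SE ratio = √(1 − R²)
- Equivalent gain in sample = 1/(1 − R²) − 1
- Power, for a contrast assumed to have 80% before the change = Φ((1.960 + 0.842)/SE ratio − 1.960)

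| Partial R² | SE ratio | SE falls by | Sample gain | Of 142.7 | Of 131.2 | Power |
|---|---|---|---|---|---|---|
| 0 | 1.000 | 0% | 0% | 0 | 0 | 80% |
| 0.02 | 0.990 | 1.0% | 2.0% | 3 | 3 | 80.8% |
| 0.05 | 0.975 | 2.5% | 5.3% | 8 | 7 | 82.0% |
| 0.10 | 0.949 | 5.1% | 11.1% | 16 | 15 | 84.0% |

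The counts refer to the two arms in a contrast because that is what each listed comparison uses. The three-arm total (246 × 0.87 = 214) would overstate them.

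**How plausible is the assumed range?** mRS and NIHSS overlap, so only the part of mRS that NIHSS does not carry counts. With m = mRS, n = NIHSS and s = SAQoL:

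partial r = (r_ms − r_ns·r_mn) / √[(1 − r_ns²)(1 − r_mn²)]

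Example: r_ms = 0.4, r_ns = 0.4 and r_mn = 0.6 give (0.4 − 0.24)/√(0.84 × 0.64) = 0.218. The interval narrows by 1 − √(1 − 0.218²) = 2.4%.

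The grid takes r_ms and r_ns at 0.3, 0.4 and 0.5, and r_mn at 0.4, 0.6 and 0.8. All these values are illustrative.
- Narrowing runs from 0% to 10.9%.
- It is at most 2.5% in 14 of the 27 combinations and at most 5% in 19.
- The 8 larger values all need r_ms = 0.5, except one: r_ms = 0.4 with r_ns = 0.3 and r_mn = 0.4, which gives 5.3%.

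The grid conditions on NIHSS only and does not account for AQ. The 10% upper case is therefore not a ceiling, but larger gains need mRS to predict SAQoL strongly and NIHSS not to.

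**Cost if mRS predicts nothing.** A useless linear covariate inflates the variance by about 1/143 = 0.7%, or about 0.35% on the SE.

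**Form of the covariate.** If the two-group form were used, a normal latent score with 50-90% of participants in the higher group keeps about 58-80% of the correlation. That is roughly 0.58² to 0.80², or 34-64% of the R².

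**The case against.** The other side has a strong case. A short adjustment set, fixed in advance and common to the primary, discourse and quality-of-life outcomes, is a legitimate choice. AQ defines the randomisation strata, and NIHSS is the stated measure of stroke severity. Leaving out one further predictor contradicts nothing in the SAP. AQ and NIHSS already absorb the part of any mRS imbalance that they share, and the confidence interval covers the chance imbalance that remains. Every size given above is an assumption, and zero is within the range. All of this stands, and it is why the point is optional.

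A reader might infer more than the document supports:
- **That precision is definitely lost.** The SAP gives no SAQoL SD and no mRS-SAQoL correlation, and says little about the content of either scale, so no loss is demonstrated.
- **That no baseline SAQoL exists.** It is not listed in the SAP, but the schedule is left to the protocol, which is not at hand.
- **That mRS will be modelled as 0-2 versus 3-6.** That split is a row in a descriptive table, and nothing carries it into a model.
- **That mRS is barred from imputation.** Missing SAQoL data follow the approach of 3.5.3, which predicts from all observed data and gives its variables only as examples. mRS is already admissible.

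The objection does not show a real drawback to adding the covariate.

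**Conclusion.** The facts hold: the SAQoL models contain baseline AQ, NIHSS and random site, no baseline SAQoL is listed in the SAP, and baseline mRS is collected but not modelled. The omission is not an error, causes no bias and leaves type I error unaffected. It may forgo a modest amount of precision on a secondary outcome: 0-2.5% on the SE of each contrast, or 5.1% in the upper case. Even the upper case would lift a contrast with 80% power by only about 4 points.

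This size rests on an assumed partial R² and, for the participant counts, on missingness borrowed from the primary outcome. Overlap between mRS and NIHSS makes the lower part of the range more likely. Priority is low. The reason to act is that the change costs almost nothing and is credible only if made before unblinding.

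**What to change.** In the quality-of-life Analysis Method, before unblinding:
1. Add baseline mRS as a covariate to both the 12-week and the 26-week SAQoL models. State that the full score enters as a single linear term (1 df), not as the Table 1 split.
2. Keep baseline AQ, baseline NIHSS and random site as planned.
3. Name baseline mRS among the predictors in the SAQoL imputation, so that the imputation and analysis models agree.

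The cost is a sentence or two in the SAP and one degree of freedom. The data are already collected. Section 1.9 says that the chief investigators and the trial statistician are blinded, so the term can still be pre-specified; added after unblinding it would look data-driven. Table 1 can stay as it is.

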1.2 Aims and hypotheses

The primary aim of the VERSE trial is to determine whether very early daily aphasia therapy (UC-Plus and VERSE groups) is superior to usual ward care at 12 weeks post stroke. The secondary aim is to test whether a standardised intense aphasia therapy regimen (VERSE) is more effective and cost effective than non-standardised intense aphasia therapy (UC-Plus). Participants are recruited within the first 14 days following stroke. For the purposes of this trial, aphasia therapy refers to direct aphasia treatment designed to change the communication performance of the person with aphasia. All analyses herewith include only direct aphasia therapy which does not include patient/family counselling and education, case management or documentation.

Primary Hypothesis:

Very early aphasia therapy will result in greater improvement in communication at 12 weeks poststroke, as measured by the Western Aphasia Battery-Revised; Aphasia Quotient (WAB-R (AQ)).²

Secondary Hypotheses:

- 1. VERSE aphasia therapy will result in a greater improvement in communication than UC-Plus aphasia therapy at 12 and 26 weeks post stroke, as measured by the WAB-R (AQ).²
- 2. VERSE aphasia therapy and UC-Plus will each result in greater improvements in communication than UC alone, as measured by the WAB-R(AQ)², at 12 weeks and 26 weeks post stroke.
- 3. VERSE aphasia therapy will result in greater improvements in connected speech than UC-Plus, as measured by Discourse Analysis, at 12 weeks and 26 weeks post stroke.
- 4. VERSE aphasia therapy and UC-Plus will each result in greater improvements in connected speech than UC alone, as measured by Discourse Analysis, at 12 weeks and 26 weeks post stroke.
- 5. Very early aphasia therapy (UC-Plus and VERSE) will result in better quality of life at 12 and 26 weeks post stroke than UC control.
- 6. Very early aphasia therapy (UC-Plus and VERSE) will be more cost-effective than UC at 12 and 26 weeks post stroke.

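### The quality-of-life analysis does not specify the combined (UC-Plus and VERSE) versus UC contrast that the SAP's own quality-of-life hypothesis calls for

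*SAP*

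**What the plan says.** SAP section 1.2 gives secondary hypothesis 5 as "Very early aphasia therapy (UC-Plus and VERSE) will result in better quality of life at 12 and 26 weeks post stroke than UC control". Section 3.7 repeats it in the same words.

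Section 3.7.2 breaks this into eight statistical hypotheses, four per visit. Item 1 is the combined comparison at 12 weeks: "Very early daily aphasia therapy (UC-Plus or VERSE) will result in higher quality of life than Usual Care alone at 12 weeks post stroke". Items 2 and 3 are VERSE versus UC and UC-Plus versus UC, and item 4 is VERSE versus UC-Plus. Items 6 to 8 repeat items 2 to 4 at 26 weeks; item 8 reads "VERSE aphasia therapy will result in higher quality of life that UC Plus at 26 weeks post stroke". Item 5, where the combined 26-week quality-of-life hypothesis belongs, reads "Very early intensive aphasia therapy (UC-Plus or VERSE) will result in greater improvements in communication ability at 26 weeks post stroke". It names another outcome and no comparator.

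The quality-of-life Analysis Method (the second section numbered 3.7.1) sets one linear mixed model for each visit. Each model makes two comparisons: "VERSE therapy to usual care alone" and "UC- Plus therapy to usual care alone". The effects to be reported are the differences "between VERSE and UC and between UC- Plus and UC".

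**The concern.** The hypothesis concerns two groups combined, but the analysis is of each group separately. Sections 3.5.2 and 3.5.4 merge UC-Plus and VERSE explicitly for the primary 12-week %MPR comparison. Section 3.7 has no matching instruction for SAQoL.

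An analyst who follows 3.7 to the letter has two p-values per visit and no rule for turning them into an answer to hypothesis 5. The hypothesis could be judged by requiring both tests, by accepting either, or by a combined contrast added later. These rules have different error rates and power, and the choice would be open after the data are seen.

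**Working it through.** **Step 1. Match each hypothesis in 3.7.2 to a contrast in the Analysis Method.**

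| Item | Comparison | Visit | Contrast listed in 3.7? |
|---|---|---|---|
| 1 | Combined vs UC | 12 weeks | No |
| 2 | VERSE vs UC | 12 weeks | Yes |
| 3 | UC-Plus vs UC | 12 weeks | Yes |
| 4 | VERSE vs UC-Plus | 12 weeks | No (3.1 may cover it) |
| 5 | Combined; outcome written as communication | 26 weeks | No |
| 6 | VERSE vs UC | 26 weeks | Yes |
| 7 | UC-Plus vs UC | 26 weeks | Yes |
| 8 | VERSE vs UC-Plus | 26 weeks | No (3.1 may cover it) |

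Four of the eight have a listed contrast.

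**Step 2. Inputs for the size of the difference.** Section 1.7 gives 246 participants, 82 per arm (3 × 82 = 246), 80% power, two-sided 5% and 20% loss. Section 1.4 gives 1:1:1 allocation. Section 1.7 gives no SD for %MPR, so 82 per arm cannot be reproduced. It also says that no pilot quality-of-life data existed, so the SAP has no quality-of-life power figure to check. Effects below are in SD units and are assumptions.

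**Step 3. Precision.** Analysable per arm: 82 × 0.8 = 65.6. Combined group: 131.2.

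- Pairwise SE: sqrt(2/65.6) = 0.175 SD
- Combined SE: sqrt(1/65.6 + 1/131.2) = 0.151 SD
- Ratio: sqrt(1.5/2) = 0.866

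The ratio does not depend on the SD or on the number per arm. It needs only equal arms, equal loss and common variance.

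**Step 4. Power when both arms have the same effect.** 80% pairwise power corresponds to a noncentrality of 1.960 + 0.842 = 2.802. For the combined contrast this becomes 2.802/0.866 = 3.235, and the power is Φ(3.235 − 1.960) = 0.90.

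| Assumed common effect (SD) | Pairwise power | Combined power |
|---|---|---|
| 0.2 | 21% | 26% |
| 0.3 | 40% | 51% |
| 0.4 | 63% | 75% |
| 0.489 | 80% | 90% |

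**Step 5. Power when the arm effects differ.** Let r be the UC-Plus effect divided by the VERSE effect. The combined effect is (1 + r)/2 of the VERSE effect, so the combined contrast beats VERSE versus UC only if (1 + r)/2 > 0.866, that is r > 0.73. At r = 0.5, with 80% power for VERSE versus UC, the combined noncentrality is 2.80 × 0.75/0.866 = 2.43, and the power is Φ(2.43 − 1.96), about 68%.

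**Step 6. What the missing decision rule leaves open.** A simulation of one million trials per setting, with 65.6 per arm, gives the chance of declaring hypothesis 5 supported at one visit under three possible rules. Significance is two-sided.

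| True common effect | Both pairwise tests | Either pairwise test | Combined contrast |
|---|---|---|---|
| 0 | 0.9% | 9.0% | 5.0% |
| 0.3 SD | 24% | 57% | 51% |

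At 0.3 SD, exactly one pairwise test is significant in 32% of trials.

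**The case against.** The best defence is that hypothesis 5 means each arm separately, so the two pairwise contrasts cover it. The SAP's own usage is against this. Where section 1.2 means separate arms it says so: "VERSE aphasia therapy and UC-Plus will each result in greater improvements in communication than UC alone". Section 3.7.2 also lists the combined hypothesis apart from the two arm-specific ones.

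Other parts of the defence stand:

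- Each planned model already contains both comparisons with UC, so the combined estimate can be formed from coefficients that will be fitted anyway. The gap is one of specification; no data or model is lacking.
- Section 3.1 says that differences among the three arms will be tested for every endpoint. That arguably covers VERSE versus UC-Plus on SAQoL (items 4 and 8), so a reader should not conclude that these have no analysis at all. The rule does not create a combined contrast.
- A reader might infer from item 5 that the combined 26-week quality-of-life hypothesis is nowhere stated. It is stated in 1.2 and 3.7. The heading above item 5 and its place in the list mark it as a copying slip.
- A reader might also infer that communication at 26 weeks is never estimated, or that a combined 26-week %MPR test is owed. Section 3.6.2.2.1 compares each early-therapy arm with UC on %MPR at 26 weeks, and section 3.11 plans a forest plot of the primary-outcome effect at both visits. No communication hypothesis in 1.2 or 3.6 calls for a combined 26-week test.

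**Conclusion.** The concern holds as a gap between hypothesis and analysis. The SAP states a combined quality-of-life hypothesis at 12 and 26 weeks, specifies its contrast at neither visit, and gives no rule for a split pairwise result. Item 5 of 3.7.2 carries the wrong outcome, and items 4 and 8 rely on a general rule that 3.7 does not repeat.

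The combined SE is 0.866 of the pairwise SE under equal arms, equal loss and common variance. The rise from 80% to about 90% power also requires equal effects in the two arms. It should not be read as a general advantage, because items 4 and 8 themselves hypothesise that VERSE is better than UC-Plus. The case for the contrast is that it matches the stated hypothesis, whether or not it is the more powerful test.

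SAQoL is a secondary outcome, and section 3.1 treats secondary analyses as supplementary and unadjusted. The primary analysis is untouched. The correction should be made before unblinding.

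**What to change.** In the quality-of-life Analysis Method, specify one three-arm model per visit, with the covariates and site effect already planned. Report four SAQoL contrasts from it, each with a 95% confidence interval:

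1. Combined UC-Plus and VERSE versus UC, named as the test of secondary hypothesis 5, with its weights stated (for example, the mean of the two arm-versus-UC differences)
2. VERSE versus UC
3. UC-Plus versus UC
4. VERSE versus UC-Plus

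Reword item 5 of 3.7.2 to quality of life versus UC at 26 weeks.

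The cost is a few lines of SAP text. The contrasts come from the three-arm model, with no change to design, sample size or data collection. No combined 26-week %MPR test needs to be added.
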